Heart Rate Response to Regadenoson and Sudden Cardiac Death

Study Protocol & Statistical Analysis Plan

NCT01842035

January 14, 2021

[name] Principal Investigator
University of Alabama at Birmingham
Birmingham, AL 35294

Heart rate response to regadenoson and sudden cardiac death

Objectives:

The main objectives of this proposal are to investigate whether:

1. A blunted heart rate response to regadenoson is an independent predictor of sudden cardiac death.
2. A blunted heart rate response to regadenoson can be used as a predictor of response to implanted cardiac defibrillator (ICD) on top of traditionally used indicators.

Hypotheses:

1. Patients with a blunted heart rate response to regadenoson are at higher risk of sudden cardiac death (death or appropriate cardiac defibrillation). This risk is maintained after controlling for age, gender, left ventricular ejection fraction, heart failure symptoms and medication use.
2. Patients with a normal heart rate response to regadenoson have a low rate of events (death or appropriate cardiac defibrillation) despite meeting current indications for having an ICD.

Background:

In patients with left ventricular systolic dysfunction and in those with a history of sudden cardiac death, an ICD reduces mortality.¹⁻³ However, not all patients with an ICD receive appropriate therapy from it (In a large study, only one third of patients received appropriate therapy from an ICD over the first 3 years of follow-up)⁴, and inappropriate ICD shocks are common and are associated with worse quality of life and increased mortality.⁵ Furthermore, ICDs are expensive (the procedure costs ~\$35,000) and place a toll on the health care system. Establishing a better predictor of risk of sudden cardiac death and of response to ICD is desirable.

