Adenosine and regadenoson are routinely used as pharmacological stress agents to induce coronary hyperemia for myocardial perfusion imaging (MPI) in lieu of exercise. The increase in heart rate seen during adenosine infusion has previously been attributed to its vasodilatory effect on the systemic circulation and has thus generated little interest. Recently, it was recognized that this rise in heart rate is related to a direct stimulation of the sympathetic nervous system by adenosine therefore allowing for a novel simple method for the evaluation of autonomic function.⁶ Using data from the ADenoscan Versus RegAdenoson Comparative Evaluation for Myocardial Perfusion Imaging (ADVANCE MPI 1 and 2) Trials, we demonstrated that patients with diabetes mellitus have a blunted heart rate response to adenosine presumably due to cardiac autonomic dysfunction.⁷ Furthermore, the heart rate response associated with multiple risk factors of sudden cardiac death.^{7, 8} Since cardiac autonomic dysfunction has been linked to increased

cardiovascular risk,⁹ we postulated that the heart rate response may carry useful prognostic information. Recently we showed that a blunted heart rate response to adenosine is associated with increased mortality in the overall population and that it assisted in the risk stratification of patients at high risk (such as those with diabetes mellitus or chronic kidney disease) when added to traditional MPI findings.¹⁰ In a Cox regression model, a blunted heart rate response was the strongest predictor of mortality and provided additional prognostic data to MPI after controlling for age, gender, race, history of myocardial infarction, diabetes mellitus, chronic kidney disease and beta-blocker use. We also demonstrated that a decreasing heart rate response to regadenoson is associated with stepwise increase in mortality.¹¹ In a Cox proportional model for mortality that adjusted for age, gender, diabetes mellitus, renal disease and MPI findings, heart rate response to regadenoson in the lowest quartile was independently associated with 5-fold increase in mortality compared to the highest quartile. Patients with a normal heart rate response had a relatively low annualized total mortality despite the presence of risk factors.

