In a recent study from our group, patients with ICD implanted for primary prevention at our center experienced an event rate of death or first appropriate ICD therapy ~ 20% over first 2 years.¹⁵ In our recent study on the heart rate response to regadenoson, patients in the lowest heart response tertile experienced a 4-fold increased risk of death compared to those in the highest tertile.¹¹ We believe that is a conservative estimate of risk for this study since the heart rate response should be a better predictor of sudden cardiac death than overall mortality. A sample size of 126 patients will provide a 90% power to detect a 4-fold increase in risk of the primary outcome for patients in the lowest compared to the highest tertile of the heart rate response to regadenoson (40% vs. 10% over 2 years) at a preset P value of 0.05. We plan for a sample size of 150 to account for any dropouts and or loss of follow-up.

Statistical Plan:

All statistical analyses will be carried out using SPSS version 17 for Windows (SPSS Inc., Chicago, Illinois). We will collect data on patient demographics (age, gender, race, education), patient characteristics (height, weight), co-morbidities (history of myocardial infarction, diabetes mellitus, hypertension, dyslipidemia, atrial fibrillation, stroke), prior cardiovascular procedures (percutaneous coronary intervention or coronary artery bypass grafting), habits (tobacco use), symptoms (NYHA classification), medication intake (aspirin, beta-blocker, calcium channel blocker, angiotensin converting enzyme inhibitor (ACE-I), angiotensin receptor blocker (ARB), aldosterone antagonist, loop diuretic, statin, insulin), electrocardiographic characteristics (left bundle branch block, right bundle branch block, QRS, QT, PR) and laboratory results (serum creatinine, electrolytes, brain natriuretic peptide).

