The population will be divided into 3 groups with 50 patients in each group based on tertiles of the heart rate response on regadenoson. Continuous variables will be presented as mean \pm SD and discrete variables as frequencies and percentages. The chi-square test or an analysis of variance (ANOVA) will be used for the comparison of categorical variables. Continuous variables will be compared using the unpaired student t test or the Mann-Whitney U test, as appropriate. In order to determine the predictors of the HRR to regadenoson, a linear regression model will be constructed with the HRR as the dependent variable and all the characteristics that are associated with the HRR ($p < 0.2$) as independent variables. An estimation of the effect of each of the variables on the HRR will be determined based on the coefficient of the variable in the regression equation. Follow-up time will be calculated from the time of evaluation to sudden cardiac death or to end of follow-up censored at 2 years from time of evaluation. Event-free survival curves will be constructed using the product-limit method (Kaplan-Meier) and differences among survival curves will be estimated by the log-rank test. Cox proportional hazard analysis will be used to estimate unadjusted and age, gender and LVEF adjusted (multivariate) risks for sudden cardiac death. We will introduce interaction terms to test for interaction between HRR and the different variables in the model. Estimated risks will be reported as hazard ratios (HR) with correspondent 95% confidence intervals (CI). All tests will be 2-tailed, and a p value of < 0.05 will be considered statistically significant.

Amendments

During the conduction of the trial, the following amendment were introduced:

1. The original protocol enrolled patients with a clinical indication for an implanted cardiac defibrillator (ICD) for primary prevention of sudden cardiac death. We amended the protocol to enroll patients who are undergoing an ICD implantation or a generator exchange for clinical indications.

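### The age, gender and LVEF model cannot by itself support an independent-predictor claim: it leaves out diabetes, renal function and two covariates that hypothesis 1 promises

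*Combined protocol and SAP*

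**What the plan says.** Objective 1 asks whether "A blunted heart rate response to regadenoson is an independent predictor of sudden cardiac death". Hypothesis 1 then states what the association has to survive: "This risk is maintained after controlling for age, gender, left ventricular ejection fraction, heart failure symptoms and medication use".

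The Statistical Plan gives a shorter list: "Cox proportional hazard analysis will be used to estimate unadjusted and age, gender and LVEF adjusted (multivariate) risks for sudden cardiac death". Nothing else in the plan widens it. The p < 0.2 selection rule belongs to the linear model in which heart rate response is the dependent variable. The interaction terms concern variables already in the Cox model. The Amendments do not touch the covariates.

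The Background reports that "patients with diabetes mellitus have a blunted heart rate response to adenosine presumably due to cardiac autonomic dysfunction". It gives as examples of high risk "patients at high risk (such as those with diabetes mellitus or chronic kidney disease"). It also describes two Cox models for mortality from the same group. The adenosine model was fitted "after controlling for age, gender, race, history of myocardial infarction, diabetes mellitus, chronic kidney disease and beta-blocker use". The regadenoson model is introduced with "In a Cox proportional model for mortality that adjusted for age, gender, diabetes mellitus, renal disease and MPI findings".

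The data needed are on the collection list in the Statistical Plan: diabetes among the co-morbidities, NYHA class, medication including beta-blockers, and "laboratory results (serum creatinine, electrolytes, brain natriuretic peptide").

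**The concern.** To call a marker an independent predictor is to say that it carries information beyond the known predictors. That statement is only as good as the covariates in the model behind it. Here the protocol itself describes a variable, diabetes, that is linked both to the exposure and to high risk, and the outcome model leaves it out. Renal disease is described as high risk, was adjusted for twice before, and is also left out. No reason is given for dropping either.

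Separately, the Statistical Plan does not deliver the adjustment that hypothesis 1 names, because symptoms and medication are missing from the Cox model.

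At stake is the study's first conclusion. If patients in the lowest tertile have diabetes more often, and diabetes raises the event rate, part of the hazard ratio credited to heart rate response belongs to diabetes. A reader could not tell how much.

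**Working it through.** **1. The plan's own figure.** The Sample Size section gives 126 patients for 90% power, 40% against 10%, two-sided 0.05. With pooled variance and no continuity correction:

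n per tertile = [1.96·√(2·0.25·0.75) + 1.2816·√(0.4·0.6 + 0.1·0.9)]² / 0.30² = [1.200 + 0.736]² / 0.09 ≈ 41.7, so 42. Three tertiles give 42 × 3 = 126.

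The figure reproduces. The calculation compares two unadjusted proportions and makes no allowance for covariates.

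**2. The adjustment sets side by side.**

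| Covariate | Statistical Plan Cox model | Hypothesis 1 | Earlier adenosine model | Earlier regadenoson model | Collected |
|---|---|---|---|---|---|
| Age, gender | yes | yes | yes | yes | yes |
| LVEF | yes | yes | not named | not named | used for eligibility |
| Diabetes | no | no | yes | yes | yes |
| Renal disease | no | no | yes | yes | serum creatinine |
| Heart-failure symptoms | no | yes | not named | not named | NYHA class |
| Medication | no | yes | beta-blocker | not named | yes |

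For diabetes, the Background supplies both links needed for confounding (to the exposure and to risk). For renal disease it supplies only the link to risk and the precedent of earlier adjustment.

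**3. Possible size for diabetes alone.** The documents give neither the prevalence of diabetes by tertile nor its effect on the endpoint, so these inputs are assumptions: prevalence p1 of 50–60% in the lowest tertile, p0 of 20–30% in the highest, diabetes risk ratio RR of 1.5–2.5. For a binary confounder:

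bias factor = [1 + p1(RR − 1)] / [1 + p0(RR − 1)]

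- Smallest: (1 + 0.5 × 0.5) / (1 + 0.3 × 0.5) = 1.25 / 1.15 = 1.09. A 4-fold ratio becomes 4 / 1.09 ≈ 3.7.
- Middle (55% v 25%, RR 2): 1.55 / 1.25 = 1.24, and 4 / 1.24 ≈ 3.2.
- Largest: (1 + 0.6 × 1.5) / (1 + 0.2 × 1.5) = 1.90 / 1.30 = 1.46, and 4 / 1.46 ≈ 2.7.

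The formula applies to a crude risk ratio. The planned estimate is a hazard ratio already adjusted for age, gender and LVEF, so any overlap of diabetes with those three would change the factor.

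**4. Cost in events per parameter.** At 150 patients, take 20% (the centre's two-year rate quoted in Sample Size, which is for all deaths plus device therapy) to 25% (the mean of 40% and 10%, assuming the middle tertile lies halfway). That is 150 × 0.20 = 30 to 150 × 0.25 = 37.5 events.

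- Planned model: two tertile terms + three covariates = 5 parameters; 30/5 to 37.5/5 = 6.0 to 7.5.
- Plus diabetes and creatinine: 7 parameters; 4.3 to 5.4.
- Plus NYHA class as one term and beta-blocker use: 9 parameters; 3.3 to 4.2.

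Amendment 3 shortens follow-up and reduces the sample size without giving the new number, so the actual figures will probably be lower.

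**The case against.** Five points can be made for the plan.

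**Few events.** A short covariate list is a defensible response to some 30 events. This stands as a constraint on how the fuller model is fitted. It does not justify claiming independence from a model that omits a confounder the protocol describes.

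**Diabetes was never promised.** Hypothesis 1 does not list diabetes or renal function. That is correct, and adding them is a reviewer's judgement. But hypothesis 1 does list symptoms and medication, which the Cox model drops, so the adjustment set has to be revisited in any case.

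**Over-adjustment.** One could argue that diabetes acts through heart rate response. The exposure here is heart rate response, and diabetes lies upstream of it. Adjusting for diabetes does not remove the effect of the response.

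**The association survived adjustment before.** In the earlier regadenoson study the lowest quartile still carried a 5-fold mortality after adjustment for diabetes and renal disease. This is fair evidence against a purely spurious result. It concerns mortality in patients having perfusion imaging, however, not sudden death or device therapy in ICD patients. For the same reason, adding two covariates would not make the new estimate directly comparable with the earlier ones.

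**The evidence on risk is indirect.** The Background speaks of high risk and mortality. It does not say that diabetes or renal disease raises the rate of this primary endpoint. This stands, and it is why the conclusion is *may*.

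A reader might go further and infer that the hazard ratio is bound to be overstated, or might count renal disease as a second factor of equal size and square the middle factor (1.24² = 1.54). The documents do not support either step. Nowhere do they say that renal disease blunts the response, and squaring also treats the two conditions as independent.

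**Conclusion.** The point holds in a limited form. The only adjusted Cox model is too narrow to carry the independent-predictor conclusion: it omits diabetes, which the Background links to both exposure and risk; renal disease, which it links to risk; and the symptom and medication covariates that hypothesis 1 names. The adjusted hazard ratio may be partly confounded.

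The amount is not derivable from the documents. Under the assumed inputs, diabetes alone would inflate the ratio by about 1.09 to 1.46. That would shrink a 4-fold association to between about 3.7 and 2.7 and would not remove it. The study is not invalidated. What needs repair is the basis for the word independent.

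**What to change.** In the Statistical Plan, keep the tertile definition of exposure and keep the age, gender and LVEF model as planned. Add a second, pre-specified Cox model with those three covariates plus diabetes (yes/no), serum creatinine, NYHA class and beta-blocker use, and state that the conclusion for objective 1 rests on this model. Say which medications count as the medication control of hypothesis 1, so that the hypothesis and the model agree.

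State in advance how the model is fitted if events are few: Firth-type penalised likelihood with matching 95% intervals, or one baseline risk score in place of the separate covariates. With a score the model has 2 + 1 = 3 parameters, or 30/3 = 10 to 37.5/3 = 12.5 events per parameter at 150 patients. This gain is real only if the score's weights are not themselves estimated freely from the same events. Switching the main exposure to continuous heart rate response would save a parameter, but it would change the exposure on which the sample size rests, and it is not needed.

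**Cost.** No new data are required. The interval will be wider. Events per parameter fall to about 4.3–5.4 with diabetes and creatinine and 3.3–4.2 with all four additions at 150 patients, and probably lower after Amendment 3. Penalised Cox regression may need software other than the SPSS version named in the plan. If the fuller model proves too imprecise to be informative, the report should say so and describe the association as adjusted for age, gender and LVEF only.

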We propose that patients with a blunted heart rate response to regadenoson have an altered autonomic nervous system (cardiac autonomic neuropathy) that places them at higher risk of sudden cardiac death. Using this novel and easily measured parameter, we will be able to select patients who are high risk and will benefit from an ICD and, at the same time, identify patients who are at low risk of experiencing sudden cardiac death despite satisfying current criteria for having an ICD (mainly a low left ventricular ejection fraction). In this proposal, we will be able to verify this using a highly selected population that is being continuously monitored for the occurrence of ventricular arrhythmias through their implanted devices.

Study Design: Prospective Observational

Population:

A total of 150 patients (18-80 years) with an indication for ICD implantation for primary prevention of sudden cardiac death as defined in the current American College of Cardiology/American Heart Association/Heart Rhythm Society Practice Guidelines.¹² Specifically we will recruit:

1. Patients with left ventricular ejection fraction (LVEF) less than 35% due to prior myocardial infarction who are at least 40 days post--myocardial infarction and are in NYHA functional Class II or III.
2. Patients with nonischemic dilated cardiomyopathy who have an LVEF less than or equal to 35% and who are in NYHA functional Class II or III.
3. Patients with LV dysfunction due to prior myocardial infarction who are at least 40 days post--myocardial infarction, have an LVEF less than 30%, and are in NYHA functional Class I.

Protocol

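### Hypothesis 1 promises control for five factors, but the only adjusted outcome model the plan specifies contains three; heart failure symptoms and medication use are left out

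*Combined protocol and SAP*

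**What the plan says.** Objective 1 puts the question to be answered: "A blunted heart rate response to regadenoson is an independent predictor of sudden cardiac death". Hypothesis 1 first states that a blunted response carries a higher risk, and then adds: "This risk is maintained after controlling for age, gender, left ventricular ejection fraction, heart failure symptoms and medication use".

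The Statistical Plan describes the adjusted outcome analysis in one sentence, as a Cox model for "unadjusted and age, gender and LVEF adjusted (multivariate) risks for sudden cardiac death". It continues: "We will introduce interaction terms to test for interaction between HRR and the different variables in the model". The only other multivariable analysis has a different outcome: "a linear regression model will be constructed with the HRR as the dependent variable".

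Both of the missing factors are to be recorded. The data list in the Statistical Plan includes "symptoms (NYHA classification), medication intake (aspirin, beta-blocker" and seven further drugs or classes, nine in all.

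**The concern.** In an observational study, the word independent can mean no more than the covariates in the model. Hypothesis 1 is the only place where the documents say which factors the risk should be independent of, and it names five. The analysis meant to deliver that result adjusts for three.

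Two things are at stake. A report that repeated the hypothesis as confirmed would claim more than the planned analysis had tested. And if someone notices the gap only at the reporting stage, the medication terms would be chosen after the results are known, from nine candidates.

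**Working it through.** **The mismatch.** This is a comparison of text and needs no arithmetic.

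| Factor | Named in Hypothesis 1 | Available | In the Cox model |
|---|---|---|---|
| Age | yes | yes | yes |
| Gender | yes | yes | yes |
| LVEF | yes | yes (eligibility) | yes |
| Heart failure symptoms | yes | yes (NYHA class) | no |
| Medication use | yes | yes (nine drugs or classes) | no |

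Three of the five factors are modelled.

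**Does another part of the plan fill the gap?**

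- *Linear regression.* It may show whether NYHA class or a drug is related to heart rate response, which is one condition for confounding. Its outcome is not sudden death.
- *Interaction terms.* They concern effect modification by variables already in the model and name no new covariate.
- *Kaplan-Meier curves and log-rank test.* These are unadjusted. Comparing characteristics across tertiles describes imbalance without correcting for it.
- *Secondary analyses (Protocol, step 1) and secondary endpoints.* A continuous version of the response, fixed cut-offs and four further endpoints are planned, with no covariates given.
- *Withholding drugs on the test morning.* This bears on how the response is measured. It is not adjustment for long-term treatment.
- *Eligibility (Population).* Item 2 takes patients "who have an LVEF less than or equal to 35% and who are in NYHA functional Class II or III", and item 3 admits those who "have an LVEF less than 30%, and are in NYHA functional Class I". This narrows the range of symptoms and links NYHA class partly to LVEF, but classes II and III stay mixed. Amendments 1 and 2 widen the population without restating NYHA limits.
- *Amendments.* None changes the covariates.

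**The plan's own sample size.** Inputs from Sample Size and the Statistical Plan: 40% vs 10%, two-sided 0.05, 90% power. Per tertile, n = [1.960 × √(2 × 0.25 × 0.75) + 1.282 × √(0.24 + 0.09)]² / 0.30² = 41.7, so 42, and 42 × 3 = 126. This matches the stated figure. The calculation is an unadjusted comparison of two groups, so the covariate question does not affect it.

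**What the extra terms would cost.**

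- Overall event rate. Sample Size cites about 20% over 2 years. With 40% and 10% in the outer tertiles and the middle tertile anywhere between them, the overall rate lies between (40 + 10 + 10)/3 = 20% and (40 + 40 + 10)/3 = 30%.
- Events: 0.20 × 126 = 25.2 up to 0.30 × 150 = 45.
- Parameters. The plan does not state how response is coded in the Cox model; I assume two tertile terms. Planned model: 2 + 3 = 5. With one NYHA term and one medication term: 7. With NYHA as two terms: 8. With one NYHA term and all nine drugs: 15.

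| Parameters | At 25.2 events | At 45 events |
|---|---|---|
| 5 (planned) | 5.0 | 9.0 |
| 7 | 3.6 | 6.4 |
| 8 | 3.2 | 5.6 |
| 15 | 1.7 | 3.0 |

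Two points could lower these figures. First, Amendment 3 reduces sample size and follow-up by an amount it does not state. Purely as an assumption, 75 to 100 patients followed for 2 years at 20-30% would give 15 to 30 events: 3.0 to 6.0 per parameter with five and 2.1 to 4.3 with seven. Second, the cited 20% is for death or first appropriate ICD therapy, while the definition under Endpoints leaves out non-sudden deaths. Hypothesis 1 describes the event differently, as death or appropriate defibrillation, so the documents do not settle how much this matters.

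**The case against.** The best defence is that three covariates is a sensible number for 25 to 45 events, and that eligibility already limits the spread of symptoms. Both points are fair. The first supports keeping the three-covariate model, but it does not support pairing that model with a five-factor hypothesis. The second is partial control only, and its extent after Amendments 1 and 2 is unknown.

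It is also fair to say that Objective 1 does not itself define independence, and that the secondary analyses are silent on covariates. So the text supports the statement that no *specified* outcome model contains NYHA class or medication. It does not support saying that none would ever be fitted.

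A reader might infer more in three directions.

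- *That Hypothesis 1 goes untested.* It does not: its first sentence is tested by the log-rank test and the Cox model. Only the second sentence is affected, and only for two factors.
- *That the association would prove to be confounding.* No document figure gives the prevalence of either factor by tertile or its effect on sudden death.
- *That an effect of the planned size would safely survive.* This fails for the same reason. The planned rates imply a hazard ratio of ln(0.6)/ln(0.9) = 4.85. Assume one omitted binary factor with hazard ratio h = 1.5 to 2.5, present in 50-70% of one outer tertile and 30% of the other. The bias factor (1 + p₁(h − 1))/(1 + p₀(h − 1)) is then 1.09 to 1.41, which leaves 3.4 to 4.5. Two such independent factors give 1.18 to 2.00, which leaves 2.4 to 4.1. If the imbalance runs the other way, the bias is towards no effect. The answer depends entirely on the assumptions, so no conclusion should be drawn.

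**Conclusion.** The point holds as an inconsistency between hypothesis and analysis. As written, the plan leaves the persistence of risk untested for heart failure symptoms and medication use. That rests on reading the two covariate lists together and needs no assumption. The unadjusted comparison stands.

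This should be put right before outcomes are analysed, because independence is the stated aim of Objective 1 and the data needed are already being collected. It is not grounds for calling the three-covariate model wrong. The events-per-parameter figures bear only on which remedy is feasible. They depend on the assumed tertile coding and on the plan's rates and sample size before Amendment 3.

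**What to change.** Reconcile the two covariate lists.

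Keep the Cox model with age, gender and LVEF as planned. Add one prespecified supplementary Cox model that also includes NYHA class and a short, named set of medication terms. Beta-blocker use is an obvious candidate, since the Background reports that the group's earlier adenosine mortality model adjusted for it. State the coding of each term and make sure it covers the patients brought in by Amendments 1 and 2. Claim independence only from the factors actually in the model. Entering all nine drugs separately is not advisable on the event counts shown.

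If too few events are expected after Amendment 3, narrow Hypothesis 1 and the independence wording of Objective 1 to age, gender and LVEF instead.

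If outcomes are already known, label the five-factor model post hoc.

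The supplementary model costs a paragraph of SAP text and one analysis of data already collected, at the price of a less stable estimate. Narrowing the wording needs no new analysis but gives up part of the claim.
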